A further sensitivity analysis will be performed to assess the impact of the COVID-19 pandemic on the primary efficacy analysis. To this end, for each subject with missing values due to COVID-19 pandemic (i.e., in case visits not performed due to COVID-19 or performed virtually due to COVID-19 so that live assessments by investigator could not be performed or discontinuation due to COVID-19 before relapse to baseline status), it will be checked whether values are missing from one or more visits directly preceding the visit when relapse to baseline was observed. While intermittently missing values due to COVID-19 (as well as continuous missingness resulting from premature discontinuation due to COVID-19) are generally assumed to be missing at random, this specific pattern of intermittent missingness might lead to bias in assessment of duration of effect. Specifically, the time to relapse to baseline status might be overestimated. Therefore, a sensitivity analysis will be conducted with time to relapse to baseline status from affected cases being censored at the first visit of those subsequent visits with missing values that directly precede the visit when relapse to baseline was observed. By this means, any overestimation of duration of effect resulting of a possibly delayed observation of relapse to baseline will be ruled out. If the first visit of those subsequent visits with missing values that directly precede relapse was performed virtually due to COVID-19 pandemic, the actual visit date will be used for censoring. In case the respective visit was not performed due to COVID-19 pandemic, time to relapse will be censored at the nominal visit date (calculated as injection date + number of days according to visit schedule in the study protocol - 1). The censoring variable CSNR will be set to 3.

The need for further sensitivity analyses was discussed during BDRMs. During the BDRM for the final analysis performed on 7-JAN-2021, it was confirmed that all randomized subjects fulfill the

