requirements to be included in the FAS. Furthermore, details on premature study discontinuations, amount, patterns and reasons for missing data on the FWS at maximum frown as assessed by the investigator and relatedness to COVID-19 pandemic as well as any identified intercurrent events were closely reviewed and discussed. It was concluded that the assumption of random missingness underlying the primary duration of effect analysis appears reasonable and that the above-specified analysis to account for a specific pattern of missingness due to COVID-19 pandemic was deemed adequate and sufficient to assess the impact of the COVID-19 pandemic on the primary efficacy analysis (see also section 7.4.7 below). No intercurrent events with relevant impact on interpretation of analysis results were identified. Thus, no additional sensitivity analyses were considered necessary.

[figure not shown]

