7.1.2 Secondary Efficacy Variables

[figure not shown]
The secondary duration of effect variables (see section 6.1.2) will be analyzed in analogy to the primary efficacy variable. However, for the final analysis, the Cox regression analysis will be limited to pooling the 20 U groups of both stages.

Duration of effects for each definition will be calculated as described in section 7.1.1, timing and censoring variables will be defined in analogy to the primary efficacy variable.

Kaplan Meier and Cox regression analyses will be performed as described above, except for the sensitivity analysis with separate 20 U groups from stage 1 and 2, which will be only done for the primary variable.

For the percentages of subjects fulfilling the criteria as described in the secondary efficacy variables (see section 6.1.2), two-sided 95% Pearson-Clopper confidence intervals will be computed for percentages of subjects showing an effect in each dose group.

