7.4.1 Discontinuations and Missing Data

[figure not shown]
With relevance to efficacy objectives, the treatment will be applied only once and hence cannot be discontinued. Therefore, no premature discontinuation from treatment can occur. Missing values likewise occur at random or because the subject completes the study early due to relapse to baseline. The latter will not impact the primary analysis of duration of effect since this was completely captured. Hence, for any Kaplan-Meier or Cox regression analysis and inferential statistics, intermittent missing data will be ignored and monotone missingness be considered as censored.

Intermittently missing values due to COVID-19 pandemic (resulting from missing visits not performed due to COVID-19 pandemic or visits performed virtually due to COVID-19 pandemic, thus precluding live assessments by the investigator as needed for the primary efficacy variable) as well as monotonously missing values resulting from premature discontinuation due to COVID-19 pandemic are as well considered missing at random. However, a specific pattern of missing values might introduce bias to assessment of the primary variable of duration of effect: If data are missing from visits directly preceding the visit when relapse to baseline status is observed, time to relapse to baseline status might be overestimated. A sensitivity to assess such impact on missing

values due to COVID-19 pandemic on the primary duration of effect variable is described in section 7.1.1.

Handling of missing values due to the COVID-19 pandemic

Due to the COVID-19 pandemic, a considerable amount of missing data is expected for subjects from stage 2. Restrictions related to COVID-19 in both the US and in Germany (temporarily closed sites, stay-at-home orders, quarantines imposed to subjects suspected to be infected) may make it impossible for many subjects to attend all planned on-site visits. Since live assessments by investigators cannot be performed remotely, this will inevitably lead to missing data.

Handling of missing data due to the COVID-19 pandemic in the final statistical analysis will depend on the number and pattern of missing values, which will be thoroughly described in the clinical study report.

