Also, reasons for missing data will be described. As specified in CSP amendment 2, for each planned study visit that was not performed at the study site, the site staff should document whether it was performed as virtual visit due to COVID-19 pandemic, not performed due to COVID-19 pandemic (with specific reason) or not performed (due to other reasons). Also, it should be documented if a subject is discontinued from the study due to COVID-19 pandemic, again with specific reason.

During the BDRM for the final analysis performed on 7-JAN-2021 (see also section 7.1.1 above and section 7.4.7 below), the sensitivity analysis described in section 7.1.1 to account for a specific pattern of missingness due to COVID-19 pandemic was considered adequate and sufficient to assess the impact of COVID-19 pandemic on primary efficacy analysis. No additional sensitivity analyses were deemed necessary by BDRM participants.

7.4.2 *Interim Analyses*

[figure not shown]
Dose Escalation Meeting

A blinded evaluation of safety data was performed on 24th July 2019 in a DEM when all enrolled subjects for stage 1 had their Day 30±7 Follow-up Observational Visit V4 completed. Based on the stage 1 data, a decision to proceed with stage 2 of the study with a dose group of 100 U NT 201 was made. The evaluation included blinded safety data of stage 1 subjects of the 20 U, 50 U, and 75 U NT 201 dose group up to Follow-up Observational Visit V4, Day 30±7.

For this DEM the following data was presented overall for the pooled blinded data:

- Subject disposition and demographic data
- Listings of medical history, concomitant diseases, previous and concomitant treatments
- Incidences of TEAEs, TEAESIs, TESAEs, related TESAEs and related TEAEs by SOC and PT
- Listings of TEAE, TEAESIs, TESAEs, Deaths and AEs leading to premature discontinuation

The DEM received complete blinded safety data of stage 1 subjects of the 20 U, 50 U, and 75 U NT 201 dose group up to Follow-up Observational Visit V4, Day 30±7. Based on the stage 1 data, it was decided to proceed with stage 2 of the study with a dose group of 100 U NT 201.

Interim Analysis after Day 180 of stage 1

An interim analysis of complete 180-day data (V9) of stage 1 was performed. This interim analysis served to get early insights regarding the benefit-risk assessment and duration of effect of the dose groups investigated in the stage 1. However, it was not the aim of this analysis to decide on premature termination of the study.

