As described in section 7.4.2 above, the additional interim analysis of complete MP data from stage 1 focused on the assessment of duration of effect of NT 201 according to the primary efficacy parameter and on occurrence of treatment emergent adverse events (TEAEs), especially treatment-related TEAEs, over the 360 Day follow-up period. Efficacy and safety data from stage 1, where doses up to 75 U were applied, can give further insights into the efficacy and safety profile of NT 201. Depending on the future development of the COVID-19 pandemic and related restrictions in both countries this was regarded as very valuable to decide whether resumption of on-site visits for stage 2 subjects with intermittently missing on-site visits still appeared meaningful and might outweigh the specific efforts and risks associated with travelling during the COVID-19 pandemic. Insights from the interim analysis at End of MP of stage 1 might be valuable to decide whether affected stage 2 subjects should be motivated to re-assume on-site visits after a certain time period with missing efficacy data according to investigator's assessments.

Any further additional statistical analyses planned to analyze the impact of missingness (see also section 7.4.1) and/or potential bias on data assessment due to COVID-19 pandemic (e.g. heterogeneity of stage 1 and stage 2 subjects due to COVID-19 related restrictions) were to be decided upon at the latest during the BDRM for the final analysis. During this BDRM, conducted on 7-JAN-2021 (see also section 7.1.1 above), details on premature study discontinuations, amount, patterns and reasons for missing data and relatedness to COVID-19 pandemic as well as any identified intercurrent events were reviewed and assessed. It was concluded that the assumption of random missingness underlying the primary duration of effect analysis still appears reasonable and that the planned analysis to account for a specific pattern of missingness due to COVID-19 pandemic (see section 7.1.1 above) is adequate and sufficient to assess the impact of the COVID-19 pandemic on the primary efficacy analysis. A separate analysis of U 20 Stage 1 and 20 U Stage 2 for the primary efficacy variable is already included in section 7.1.1. No

intercurrent events with relevant impact on interpretation of analysis results were identified. For these reasons, no additional sensitivity analyses were deemed necessary by BDRM participants.

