9 CHANGES TO FORMER VERSIONS

This update of the SAP became necessary due to amendment 2 of the CSP, dated 30-APR-2020. The main objective of CSP amendment 2 is to assure subjects safety during the COVID-19 pandemic and to mitigate its impact on assessments of adverse events and on assessments of secondary [REDACTED] efficacy parameters which based on subjects' self-assessment in case subjects cannot attend on-site visits during the current situation.¹⁴

The following changes to version 1.0 of the SAP were made:

- Section 2: CSP amendment 2, dated 30-APR-2020, added.
- Section 3.1: New subsection on interim analysis of complete stage 1 MP data added to the subsection on “MP: Stage 1 of the study”.

¹⁴ The primary efficacy parameter is also expected to be affected by restrictions due to the COVID-19 pandemic as mitigation measures such as, e.g., remote assessments, are not possible for live assessments by the investigator as needed for this parameter. However, subjects will be asked to come for an unplanned on-site visit at the earliest possible date that the subject is able to safely come to the site again.

- Section 6.1: New paragraph added to explain which efficacy assessments can be performed remotely and which ones will be missing if on-site visits due to COVID-19.
- Section 6.2: New paragraph added to specify that and which kind of safety data will be collected via phone in case due to COVID-19 pandemic, planned on-site visits cannot be performed.
- Section 7, second sentence: “For the interim analysis” changed to “For the interim analyses of stage 1 at Month 6 and at End of MP”.
- Section 7.4.1: New subsection “Handling of missing values due to the COVID-19 pandemic” added.
- Section 7.4.2: New subsection “Interim Analysis after End of Main Period of stage 1” added.
- Section 7.4.7 Additional analyses due to outbreak of COVID-19 pandemic added.

The following changes to version 2.0 of the SAP were made:

- Sections 6.2.1, 7.2 and 7.3: MedDRA version updated.
- Section 6.2.3: Weight and body mass index added to vital sign parameters.
- Section 6.2.3 and 7.2.3: Definition of baseline for analysis of clinical biochemistry and hematology.
- Section 7.2.3: Definition of baseline for analysis of clinical biochemistry and hematology.
- Section [REDACTED] 7.2 [REDACTED] New variables related to impact of COVID-19 pandemic on study conduct added.

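### The only COVID-19 sensitivity analysis censors subjects because they relapsed, so it can still overestimate duration of effect

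*SAP*

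**What the plan says.** SAP 7.1.1 recognises that relapse first seen after missed COVID-19 visits may be dated too late. For those cases it specifies time to relapse "being censored at the first visit of those subsequent visits with missing values that directly precede the visit when relapse to baseline was observed", and it states the result without reservation: "By this means, any overestimation of duration of effect resulting of a possibly delayed observation of relapse to baseline will be ruled out".

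All other gaps fall under SAP 7.4.1: "intermittent missing data will be ignored and monotone missingness be considered as censored". A subject who misses the same visits and returns still improved therefore stays in the risk set throughout.

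The final blind data review meeting relied on this one analysis. SAP 7.1.1 records that it "was deemed adequate and sufficient to assess the impact of the COVID-19 pandemic on the primary efficacy analysis", SAP 7.4.7 repeats that it "is adequate and sufficient to assess the impact of the COVID-19 pandemic on the primary efficacy analysis", and SAP 7.4.1 closes the matter: "No additional sensitivity analyses were deemed necessary by BDRM participants".

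For the secondary durations, SAP 7.1.2 says: "Kaplan Meier and Cox regression analyses will be performed as described above, except for the sensitivity analysis with separate 20 U groups". Only the stage split is excepted, so the COVID-19 rule can be read as carrying over. SAP 7.4.1 mentions it only for the primary variable.

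**The concern.** Kaplan-Meier, log-rank and Cox analyses need censoring that says nothing about the outcome. Here a subject is censored precisely because relapse was observed. The conclusion that the gaps are missing at random does not help, because the rule selects on relapse among subjects with gaps. One upward bias (late dating) is exchanged for another (deleted relapses).

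SAP 7.4.7 states that stage 1 subjects missed no main-period visits because of COVID-19. Stage 2 holds all 60 planned 100 U subjects but only 30 of the 60 in the pooled 20 U reference group, so any upward bias tends to favour 100 U. If the primary and sensitivity results agreed, that would be read as reassurance, although affected subjects bias both in the same direction.

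**Working it through.** **Inputs from the documents.** Planned groups are 60 (100 U) and 30 + 30 (20 U pooled). Follow-up runs to Day 360. The last subject was randomised on 10 October 2019, and the dose escalation meeting was held on 24 July 2019. Stage 2 subjects were therefore at about Day 154 to Day 229 on 11 March 2020. The base timing and censoring rules in SAP 7.1.1 are redacted. I assume relapse is dated at the visit where it is observed, as the visible text implies. The plan gives no figure of its own to reproduce.

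**Worked example (no distribution assumed).** Of 60 subjects, 40 are still improved after Day 210. Half of these (20) miss Days 240 and 270 and return on Day 300. In each half, 10 relapse by Day 300, truly at 3, 3 and 4 on Days 240, 270 and 300. The relapse-free share starts at 40/60.

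- Complete visits, Day 300: 40/60 × 34/40 × 28/34 × 20/28 = 0.333
- Primary: 40/60 × 37/40 × 34/37 × 20/34 = 0.333
- SAP rule (10 relapsers censored at Day 240): 40/60 × 37/40 × 24/27 × 20/24 = 0.457
- Event at first missed visit: 40/60 × 27/40 × 24/27 × 20/24 = 0.333

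| Day | Complete | Primary | SAP rule | Event at first missed visit |
|---|---|---|---|---|
| 240 | 0.567 | 0.617 | 0.617 | 0.450 |
| 270 | 0.467 | 0.567 | 0.548 | 0.400 |
| 300 | 0.333 | 0.333 | 0.457 | 0.333 |

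At Day 270 the SAP rule is nearer the truth than the primary analysis. From the return visit on, the primary curve is correct and the SAP curve stays too high.

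**Why the direction is fixed.** Let N be the number at risk just after one affected subject's censoring date, counting that subject. From the return visit onward, S(SAP rule)/S(primary) ≥ N/(N − 1), with equality if nobody else drops out. Converting subjects one at a time extends this to any number. In the example, 37 are at risk after Day 240 and 10 are converted: 37/36 × … × 28/27 = 37/27, and 0.333 × 37/27 = 0.457. In 4,685 simulated 60-subject datasets without other dropout, the SAP-rule curve was below the primary curve after the last return visit in none. The same held in 4,971 datasets with random dropout.

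**Size (assumed inputs).** 30-day visits; stage 2 randomised evenly from 1 August to 10 October 2019; on-site visits missed from 16 March to 31 May 2020; Weibull relapse times, shape 2.5. Mean duration to Day 360, in days, with 25% of stage 2 missing visits (difference from complete visits in brackets):

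| True median | Complete | Primary | SAP rule | Event at first missed visit |
|---|---|---|---|---|
| 120 | 138.3 | 140.8 (+2.5) | 139.6 (+1.3) | 137.6 (−0.7) |
| 150 | 169.1 | 173.1 (+4.0) | 172.0 (+2.9) | 167.0 (−2.1) |
| 180 | 199.2 | 203.6 (+4.4) | 203.8 (+4.6) | 196.0 (−3.2) |
| 210 | 226.7 | 230.8 (+4.1) | 232.5 (+5.8) | 223.1 (−3.6) |
| 240 | 250.4 | 254.0 (+3.6) | 256.6 (+6.2) | 246.9 (−3.5) |

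The SAP rule's overestimate is 0.5–2.3 days at 10% missing, 1.3–6.2 at 25% and 3.0–13.8 at 50%. It is nearer the truth than the primary analysis in 7 of 15 scenarios and further away in 8. SAP section 9 says that "subjects will be asked to come for an unplanned on-site visit at the earliest possible date"; with such a visit within 14 days of reopening, the overestimate is still 0.4–13.0 days. Varying the shape (1.5, 2.5, 4) and the end of closure (30 April to 30 June) gives 135 scenarios. The SAP rule is above the complete-visit mean in all 135 and nearer to it than the primary analysis in 61.

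**Between groups, no true dose effect** (medians 150, 210, 240 days; 10,000 trials per scenario). A hazard ratio below 1 favours 100 U. False positives favouring 100 U are 2.4–2.8% with complete visits.

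| Missing | 100 U affected, of 60 | HR primary | HR SAP rule | False positives, SAP rule |
|---|---|---|---|---|
| 10% | about 2 | 0.988–0.994 | 0.983–0.993 | 3.0–3.5% |
| 25% | 5–6 | 0.966–0.984 | 0.954–0.975 | 3.7–4.7% |
| 50% | 9–12 | 0.937–0.967 | 0.897–0.944 | 5.0–7.8% |

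A separate simulation with log-normal times, 60- or 90-day gaps and 25–100% of stage 2 affected gave larger values. The mean for 100 U was too long by 5.1–46.9 days under the SAP rule, against 2.7–24.7 in the primary analysis. Direction agrees; size depends on the assumptions.

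**The case against.** Read narrowly, the SAP sentence claims only that delayed observation no longer inflates duration, and the rule does stop late dates from entering. That reading is fair, but the SAP then treats the rule as sufficient for the pandemic's whole effect on the primary analysis, which it is not.

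The planned summary is the Kaplan-Meier median, which moves less than the mean. In simulated groups of 60, the median under the SAP rule differed from the complete-visit median in 0% of trials at a true median of 120 days, at most 0.6% at 150 and 3–25% at 180. Up to 210 days it differed no more often than the primary median; it was clearly worse only at 240 days (20–81%). This stands for the medians. The log-rank and Cox results are also planned outputs and are affected.

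The separate 20 U stage 1 and stage 2 model bears on the uneven exposure of the reference group, but leaves gap handling unchanged, including for 100 U.

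Dating relapse at the first missed visit is biased too, downward, and at 180 days it moves the median more often (8–30% against 3–25%). It therefore serves only as one bound.

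The number affected is unknown, the comparison is exploratory, and the primary estimate is untouched. All of this limits the consequence without making the rule valid. Whether the rule extends to the secondary durations is an ambiguity, not an error.

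**Conclusion.** The concern holds. Censoring under the rule depends on the outcome, and the analysis does not rule out overestimation. Confidence is high for mechanism and direction: the inequality needs no distribution, and the mean under the rule exceeded the complete-visit mean in every large-sample scenario and in about 98% of simulated 60-subject datasets.

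Size is uncertain. It rests on assumed relapse times, closure dates and missing rates, and on relapse being dated at the visit where it is seen. With about 2 affected of 60 the effect is negligible; with none, the two analyses are identical. With 9–12 of 60, the null hazard ratio shifts to 0.897–0.944. The point is worth correcting because the SAP itself expects considerable missing data in stage 2 and leans on this analysis alone.

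**What to change.** 1. In SAP 7.1.1, keep the relapse as an event. Replace the censoring rule with an event at the first missed visit, reported beside the primary analysis. For affected subjects, the two dates bracket what complete visits would have shown in each group's curve. With 0.5–2% dropout per visit, the complete-visit mean stayed inside the bracket in every dataset checked, with trivial pointwise departures (95th percentile at most 0.005).
2. Preferably add an interval-censored analysis, placing relapse between the last on-site rating showing improvement and the first on-site rating at baseline status. In the 15 scenarios with scheduled return, such an estimate was within 0.1 day of the complete-visit mean.
3. Report the number of affected subjects for 100 U, 20 U stage 1 and 20 U stage 2.
4. State in SAP 7.1.2 whether the rule applies to the secondary durations.
5. Reword the claim to say only that no late relapse date is used, and revise the sufficiency statements in SAP 7.1.1, 7.4.1 and 7.4.7 to match.

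The minimum change costs SAP wording and one altered derivation. The interval-censored analysis needs a few extra programs and a less familiar method. No new data are required.

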7.1.2 Secondary Efficacy Variables

[figure not shown]
The secondary duration of effect variables (see section 6.1.2) will be analyzed in analogy to the primary efficacy variable. However, for the final analysis, the Cox regression analysis will be limited to pooling the 20 U groups of both stages.

Duration of effects for each definition will be calculated as described in section 7.1.1, timing and censoring variables will be defined in analogy to the primary efficacy variable.

Kaplan Meier and Cox regression analyses will be performed as described above, except for the sensitivity analysis with separate 20 U groups from stage 1 and 2, which will be only done for the primary variable.

For the percentages of subjects fulfilling the criteria as described in the secondary efficacy variables (see section 6.1.2), two-sided 95% Pearson-Clopper confidence intervals will be computed for percentages of subjects showing an effect in each dose group.

